19.0 APPENDIX

- 19.1 This study will utilize the CTC (NCI Common Toxicity Criteria) version 2.X for toxicity and Adverse Event reporting. A copy of the CTC version 2.X can be downloaded from the CTEP home page (<http://ctep.info.nih.gov>). **All appropriate treatment areas should have access to a copy of the CTC version 2.X.**
- 19.2 Expanded Participation Project (EPP) Instructions
- 19.3 Returned Medication Packing Slip
- 19.4 **S9921 Novantrone® Drug Request Form**
- 19.5 Determination of Expedited Adverse Event Reporting Requirements
- 19.6 CTSU Regulatory and Monitoring Guidelines

CLOSED EFFECTIVE 01/12/2007

19.2 Expanded Participation Project (EPP) Instructions.

**ADJUVANT ANDROGEN DEPRIVATION VERSUS MITOXANTRONE PLUS PREDNISONE
PLUS ANDROGEN DEPRIVATION IN SELECTED HIGH RISK PROSTATE CANCER PATIENTS
FOLLOWING RADICAL PROSTATECTOMY**

PHASE III

1.0 EPP Randomization and Registration Procedures

- I. EPP institutions will enroll a patient on-line through the Clinical Trials Management Unit (CTMU). Questions pertaining to eligibility criteria should be directed to the CTMU, medical questions should be directed to the Study Chair.
- II. A signed HHS 310 form documenting the Institutional Review Board (IRB) approval for this study must be on file at the CTMU before the EPP institution can enter a patient. IRB approval date must be less than one year prior to the date of registration.
- III. Once eligibility is confirmed, the CTMU will contact SWOG to randomize the patient. The CTMU will notify the institution by an email upon successful registration with SWOG. In addition SWOG will forward confirmation of randomization and treatment assignment to the CTMU for routing to the participating institutions. Please check for errors, and submit any corrections in writing to the CTMU. Treatment should start within one working day after registration.

2.0 EPP Data Submission

Data must be submitted electronically directly to the CTMU according to the following schedule:

FORM	TIME OF SUBMISSION
1. SWOG Registration Form	At enrollment
2. Prostate Cancer Prestudy Form** (Pathology Report*)	Within 14 days of enrollment
3. EPP Toxicity Form	Months 1, 2, 3, and every three months while on protocol therapy
4. EPP Follow-up Form**	Every 3 months while on protocol treatment and every 6 months after completion of protocol treatment until death
5. EPP Recurrence Form	At the time of recurrence

FORM	TIME OF SUBMISSION
6. EPP Chemotherapy/Immunotherapy/Hormonal Therapy Form	At the completion of protocol therapy
7. EPP Off-Treatment Form**	At the completion of all protocol therapy
8. EPP Notice of Secondary Malignancy Form	Within 10 days of diagnosis
9. EPP Death Form	Within 7 days of knowledge of event

* Fax a copy of the Pathology Report to the CTMU Attn: EPP Protocol Monitor [contact]

** These forms are to be submitted according to the above schedule for all patients who never started treatment.

3.0 EPP Adverse Drug Reaction

For EPP Institutions, all ADR's are to be faxed to the CTMU (Attn: EPP Protocol Monitor [contact]) using the Adverse Reaction (ADR) Form for Investigational Drugs. These reports will be reviewed and directed to the Southwest Oncology Group and appropriate regulatory offices. ADR reporting is based on the revised NCI Common Toxicity Criteria (version 2.X).

+

ADRs will be faxed to the CTMU based on the following adverse event reporting requirements table:

AGENTS	GRADE				
	1	2	3	4	5
Commercial Agents Expected AE	-----	-----	-----	-----	-----
Commercial Agents Unexpected AE	-----	-----	-----	ADR	ADR

ADR = Adverse Drug Reaction Report (within 7 days)

ADR reports should be submitted via fax within 7 days of the event. These will be forwarded to the NCI and the Coordinating Group within 3 working days. All ADRs should be reported to the local IRB.

For commercially available drugs, written reporting of any increased incidence of a known ADR is also required in addition to grade 4 and 5 toxicities.

All toxicities, including those with separate reporting requirements described above, must be reported on the Toxicity Form. Deaths are required to be reported via the Death Form within 7 days of knowledge of the event.

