Appropriate symptomatic treatment of nausea and/or emesis, diarrhea, mucositis, and/or abdominal pain is permitted.

c. Cardiovascular

The total cumulative dose of mitoxantrone is anticipated to $\leq 72 \text{ mg/m}^2$; based on 6 cycles of 12 mg/m^2 ; EKG changes, arrhythmias, tachycardia, and/or chest pain should be managed based on the specific findings. Patients who have underlying cardiac disease or CHF, will undergo baseline ejection fraction determination echocardiogram or MUGA and this evaluation will be repeated for all patients every two courses. If MUGA decreases to below institutional limits (or $< 15\%$) discontinue protocol treatment.

d. Allergic:

Patients who experience Grade 3 or 4 hypotension, urticaria, or severe rash should be removed from protocol treatment.

e. Hepatic (\geq Grade 2):

Delay mitoxantrone treatment for up to 4 weeks until transient increases in SGOT or hyperbilirubinemia have resolved to Grade 1 or less. If toxicity has not resolved within 4 weeks discontinue protocol treatment.

f. Other:

If toxicities \leq Grade 2, manage symptomatically, if possible and retreat without dose reduction.

If toxicities \geq Grade 3, drug should be withheld (except for alopecia or anemia) until resolution to \leq Grade 1 or baseline if baseline was greater than Grade 1, then reinstated, if medically appropriate, at a dose of 9 mg/m^2 (permanent dose reduction).

8.4 For chemotherapy treatment or dose modification related questions please contact [name] at [name] or [name] at [name]. For urology related questions please contact [name] at [name]. For radiation therapy related questions please contact [name] at [name].

8.5 Unexpected or fatal toxicities (including suspected reactions) must be reported to the Operations Office, to the Study Coordinator, to the IRB and the NCI. The procedure for reporting adverse reactions is outlined in Section 16.0.

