16.1 Adverse Event Reporting Requirements

a. Purpose

Adverse event data collection and reporting, which are required as part of every clinical trial, are done to ensure the safety of patients enrolled in the studies as well as those who will enroll in future studies using similar agents. Adverse events are reported in a routine manner at scheduled times during a trial. (Directions for routine reporting are provided in Section 14.0.) Additionally, certain adverse events must be reported in an expedited manner to allow for more timely monitoring of patient safety and care. The following guidelines prescribe expedited adverse event reporting for this protocol. See also Appendix 19.5 for general and background information about expedited reporting.

b. Reporting methods

This study requires that expedited adverse event reporting use the NCI's Adverse Event Expedited Reporting System (AdEERS). The NCI's guidelines for AdEERS can be found at <http://ctep.cancer.gov>. An AdEERS report must be submitted to the Southwest Oncology Group Operations Office by one of the following methods:

- Electronically submit the report via the AdEERS Web-based application located at <http://ctep.cancer.gov>, or
- Only if submitting electronically is not possible, fax the completed NCI Adverse Event Expedited Report – Single Agent or Multiple Agents – paper template, located at <http://ctep.cancer.gov>, to [name]. Once Internet connectivity is restored, an AE report submitted on a paper template must be entered electronically into AdEERS by the original submitter at the site.

c. When to report an event in an expedited manner

When the adverse event requires expedited reporting, submit the report within 10 calendar days of learning of the event.

d. Other recipients of adverse event reports

The Operations Office will forward reports and documentation to the appropriate regulatory agencies and drug companies as required.

Adverse events determined to be reportable must also be reported according to local policy and procedures to the Institutional Review Board responsible for oversight of the patient.

e. **Expedited reporting for commercial agents**

Commercial reporting requirements are provided in Table 16.2. If there is any question about the reportability of an adverse event or if on-line AdEERS cannot be used, please telephone or email the SAE Program at the Operations Office, [name] or [contact], before preparing the report.

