Table 16.2. Expedited reporting requirements for adverse events experienced by patients who have received commercial drug(s) on this study.

Attribution	Grade 4		Grade 5^a	
	Unexpected	Expected	Unexpected	Expected
Unrelated or Unlikely			AdEERS	AdEERS
Possible, Probable, Definite	AdEERS		AdEERS	AdEERS
AdEERS: Indicates an expedited report is to be submitted using the NCI AdEERS Commercial Drug pathway within 10 calendar days of learning of the event.				
^a This includes all deaths within 30 days of the last dose of treatment with a commercial agent(s), regardless of attribution. Any death that occurs more than 30 days after the last dose of treatment with a commercial agent(s) and is attributed (possibly, probably, or definitely) to the agent(s) and is not due to cancer recurrence must be reported according to the instructions above.				

f. **Reporting secondary AML/MDS/ALL**

All cases of acute myeloid leukemia (AML), myelodysplastic syndrome (MDS), and acute lymphocytic leukemia (ALL) that occur in patients on NCI-sponsored trials following chemotherapy for cancer must be reported using the NCI/CTEP Secondary AML/MDS Report Form in lieu of AdEERS. The following supporting documentation must also be submitted within 30 days:

- a copy of the pathology report confirming the AML/MDS/ALL diagnosis;
- and
- (if available) a copy of the cytogenetics report.

Submit the Report and documentation to:

Investigational Drug Branch **and** Southwest Oncology Group
by fax at [contact] ATTN: SAE Program
[name]
[name]

NOTE: If a patient has been enrolled in more than one NCI-sponsored study, the AML/MDS Report must be submitted for the most recent trial.

Adverse Reaction Reporting Requirements for CALGB Institutions:

CALGB participants should employ definitions of adverse events as described above. **Adverse reactions, both written and telephone reports, should be made directly to the Southwest Oncology Group and the NCI according to the institutions in those sections. A copy of written AERs should also be sent to the CALGB Regulatory Affairs Coordinator:**

CALGB Central Office
Attn: Regulatory Affairs, Coordinator
[name]
[name]
[contact]

Institutions are responsible for notifying their IRBs of toxicities reported as adverse events under these guidelines.

Adverse Event (AE) Reporting for CTSU Investigators:

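### The EPP adverse-event table asks for no expedited report of an expected Grade 5 event, while Table 16.2 and Section 8.5 require one to be reported

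*Combined protocol and SAP*

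**What the plan says.** Two sets of expedited-reporting rules are current in the combined protocol and SAP.

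**Protocol-wide.** Section 16.1 sets expedited reporting for the protocol as a whole and names AdEERS as the system. Table 16.2 applies to patients given commercial drug on the study, with no exception for EPP sites. It shows AdEERS in every Grade 5 cell, with 10 calendar days from learning of the event. Its footnote says of Grade 5: "This includes all deaths within 30 days of the last dose of treatment with a commercial agent(s), regardless of attribution". Later deaths count only if attributed to the agent and not due to recurrence. Section 8.5 adds: "Unexpected or fatal toxicities (including suspected reactions) must be reported to the Operations Office, to the Study Coordinator, to the IRB and the NCI". It points to Section 16.0 for the procedure.

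**EPP sites.** Appendix 19.2 section 3.0 has reports faxed to the CTMU on a form titled for investigational drugs. It states: "ADRs will be faxed to the CTMU based on the following adverse event reporting requirements table". That table has two rows, "Commercial Agents Expected AE" and "Commercial Agents Unexpected AE". The first is dashed at Grades 1 to 5. The second calls for an ADR report at Grades 4 and 5. ADR reports are due within 7 days of the event and go on to the NCI and the Coordinating Group within 3 working days. Below the table stands: "For commercially available drugs, written reporting of any increased incidence of a known ADR is also required in addition to grade 4 and 5 toxicities". Deaths go on a Death Form within 7 days of knowledge, and all toxicities go on the Toxicity Form.

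**The concern.** At Grade 5, Table 16.2 does not let the expedited report depend on whether the event was expected. The EPP table does. An EPP site that follows its own table would file neither an ADR nor an AdEERS report for an expected fatal event, while another site would file one.

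At stake is the completeness of expedited safety reporting for fatal events. In the EPP section, forwarding to the NCI and the Coordinating Group is written only for ADR reports, and so is the instruction to inform the local IRB. If no ADR is called for, neither step is triggered. The matter outlasts accrual: Section 7.9 has all patients followed for 15 years or until death, and Table 16.2 keeps attributed deaths reportable after 30 days.

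**Working it through.** No sample size, power or error rate enters this point, so the check is a cell-by-cell comparison.

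**Step 1: Grade 5, table against table.**

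| Grade 5 event | EPP table (Appendix 19.2, 3.0) | Table 16.2 | Result |
|---|---|---|---|
| Unexpected | ADR within 7 days of the event, forwarded within 3 working days | AdEERS within 10 calendar days of learning, both attribution rows | Expedited on both routes |
| Expected | Dashes, no ADR | AdEERS within 10 calendar days of learning, both attribution rows | Conflict |

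Table 16.2 has 2 (expectedness) × 2 (attribution) = 4 Grade 5 cells, all marked AdEERS. The EPP table has no attribution axis, so its single dashed Grade 5 cell corresponds to 1 × 2 = 2 of those 4. By expectedness alone, 1 of 2 categories conflicts.

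**Step 2: limit of Table 16.2.** The footnote takes in all deaths within 30 days of the last dose. After that it takes in only those attributed to the agent and not due to recurrence. The conflict exists only inside that scope.

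**Step 3: does other EPP text fill the dashed cell?**

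- The Death Form does apply. It goes to the CTMU within 7 days of knowledge, which is shorter than the 10-day AdEERS limit. No onward step to the NCI or the Coordinating Group is written for it.
- The sentence on Grade 4 and 5 toxicities makes no split by expectedness and can be read as covering the case. It gives no form or clock of its own. On that reading it contradicts the dashes directly above it.

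**Step 4: does the main protocol fill it?** Section 8.5 covers every fatal toxicity and refers to Section 16.0. That section contains instructions specific to CALGB and CTSU sites but none for EPP sites. The EPP procedure is in the appendix, which uses a faxed form where 16.1b requires AdEERS. The main text therefore sets the obligation, and the appendix gives EPP sites a different and narrower procedure.

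**Step 5: number affected.** The documents give neither the number of EPP patients nor the number of their deaths. No estimate is possible, and none is offered.

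**The case against.** The strongest reply is that the protocol already covers the case. Section 8.5, Section 16.1 and Table 16.2 apply to everyone. The EPP section itself records every death within 7 days and mentions Grade 4 and 5 toxicities without qualification. On this view the dashed row is only a drafting slip. Much of this stands: the death is promptly on record, and a careful site could work out the wider duty. But the appendix is the page written for EPP sites, and its table says otherwise.

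A second reply is that the documents identify no fatal event that falls in the dashed cell. A reader might infer that deaths from mitoxantrone cardiotoxicity or myelosuppression, or from heart failure on prednisone, are expected because Section 3.0 lists those toxicities. Appendix 19.5 Step 4 does not support that: an event is also unexpected if its severity is unlisted, and Section 3.0 states no fatal severity for these. The package inserts, which might settle it, are not among the documents. This reply stands in full; the point rests on the conflict between rules, not on those examples.

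A third reply is timing. Accrual closed and mitoxantrone distribution stopped in January 2007, and the current participant list does not name EPP. This lowers the prospective value but does not remove it, given the long follow-up and the continuing duty to report attributed deaths.

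**Conclusion.** The contradiction is real and current, and it is narrow. For an expected Grade 5 event on a commercial agent, the EPP table calls for no ADR, while Table 16.2 calls for AdEERS within its footnote's limits and Section 8.5 requires fatal toxicities to be reported. The EPP section also differs from 16.1b on the system and from itself on Grade 4 and 5 toxicities. What is lost is the expedited report and its stated forwarding to the NCI and the Coordinating Group.

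Three stronger inferences are not supported:

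- **That any treatment-related death escapes expedited reporting at an EPP site.** Unexpected Grade 5 events are expedited on both routes, and every EPP death goes on the Death Form.
- **That the monitoring committee missed deaths.** Under Section 11.4 it works from the Study Statistician's reports and the primary outcome data, and deaths are primary endpoint events. The documents describe no separate tally of expedited reports.
- **That the 3 leukemia cases among 488 chemotherapy-arm patients give a scale.** Those are AML cases, not stated to be deaths. Secondary AML has its own NCI/CTEP form under both 16.1f and the EPP appendix.

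The conclusion assumes that the table entries were read correctly from the PDF and that EPP sites work from Appendix 19.2. The number of deaths affected is unknown and could be zero.

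**What to change.** Reconcile Appendix 19.2 section 3.0 with Section 16.1, Table 16.2 and Section 8.5. Replace its table, its faxed form and its sentence on Grade 4 and 5 toxicities with one instruction: EPP sites follow Section 16.1 and Table 16.2, report through AdEERS, and copy the CTMU. The 7-day limit may stay. If it does, state when the clock starts, because the EPP text counts from the event and Table 16.2 from learning of it.

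Then compare the EPP Death Forms once with the AdEERS reports and file any Grade 5 report that Table 16.2 required and that is missing.

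The cost is one appendix page and a one-time reconciliation of EPP deaths, possibly with a few late expedited reports. No endpoint, sample size or analysis changes.

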4.0 EPP Secondary Malignancy Reporting

Investigators are required to report secondary malignancies occurring on or following treatment on NCI-sponsored protocols using commercial drugs. Reporting of cases of secondary AML/MDS is to be performed using the NCI/CTEP Secondary AML/MDS Report Form. This form should be used in place of DCT Adverse Reaction (ADR) Form for reporting this toxicity. All other secondary malignancies should be reported using the form DCT Adverse Reaction Form. The EPP Notice of Secondary Malignancy must also be completed for all cases of secondary malignancy.

RETURNED MEDICATION PACKING SLIP

Institution: _____

Address: _____

Principal Investigator: _____ Phone No.: _____

Phone No.: _____

Study No: _____ **Cooperative Group No.:** _____

Cooperative Group No.: _____

Study Title: _____

Instructions:

Per FDA requirements, please retain a copy of this completed form for your files. Drug being returned for any reason should be sent, together with this original form, to UVI, Inc., c/o Livingston Healthcare Services, Inc., [name], [name]. Questions may be directed to [contact], Monday through Friday 8:00 am - 5:00 pm, Pacific Standard Time. Voice Mail is available at all other times.

Study open to patient accrual at your site?

Person Shipping Drug:

Yes No

Drug being returned by:

Are there any patients at your site still receiving treatment?

Fed Ex UPS US Mail

Yes No

Date: _____ No. of cartons: _____

Reason drug returned? (Please check one)

Data Manager's/Pharmacist's Signature:

Drug Expired

Date: _____

Unused drug being returned

Fax number:

DESCRIPTION OF RETURN SHIPMENT

Comments:

TO BE COMPLETED AT WAREHOUSE

Returned shipment received on _____ and checked by _____
(Date) (Name)

Appended 4/15/00
Revised 5/15/00
Amended 7/1/00
Revised 7/15/01

Revised 11/1/02
Revised 5/15/03
Revised 9/1/03

S9921
Page 62
Amended 2/14/06

S9921 APPENDIX 19.4

Novantrone Drug Request Form

Requested By:

Dr. _____ Dr.'s State License #* _____

Institution _____ Current IRB Approval Date _____

Principal Investigator _____

Institution Contact _____

Telephone _____ Fax _____

*Note: Actual copy of license is required from physicians from Delaware, the District of Columbia, South Dakota, Mississippi and Puerto Rico. For other states, please indicate # only.

**Novantrone will be shipped Monday through Wednesday.
A minimum of two days notice is required.**

Date Drug Needed By:

Ship to:

19.5 Determination of Expedited Adverse Event Reporting Requirements

Adverse event data collection and reporting, which are required as part of every clinical trial, are done to ensure the safety of patients enrolled in the studies as well as those who will enroll in future studies using similar agents. Adverse events are reported in a routine manner at scheduled times during a trial. (Directions for routine reporting are provided in Section 14.0.) Additionally, certain adverse events must be reported in an expedited manner to allow for more timely monitoring of patient safety and care. Expedited adverse event reporting principles and general guidelines follow; specific guidelines for expedited adverse event reporting on this protocol are found in Section 16.0.

Reporting requirements may include the following considerations: 1) whether the patient has received an investigational or commercial agent; 2) the characteristics of the adverse event including the *grade* (severity), the *relationship to the study therapy* (attribution), and the *prior experience* (expectedness) of the adverse event; 3) the Phase (I, II, or III) of the trial; and 4) whether or not hospitalization or prolongation of hospitalization was associated with the event.

An investigational agent is a protocol drug administered under an Investigational New Drug Submission (IND). In some instances, the investigational agent may be available commercially, but is actually being tested for indications not included in the approved package label.

Commercial agents are those agents not provided under an IND but obtained instead from a commercial source. The NCI, rather than a commercial distributor, may on some occasions distribute commercial agents for a trial.

When a study includes both investigational and commercial agents, the following rules apply.

- *Concurrent administration:* When an investigational agent(s) is used in combination with a commercial agent(s), the combination is considered to be investigational and expedited reporting of adverse events would follow the guidelines for investigational agents.
- *Sequential administration:* When a study includes an investigational agent(s) and a commercial agent(s) on the same study arm, but the commercial agent(s) is given for a period of time prior to starting the investigational agent(s), expedited reporting of adverse events that occur prior to starting the investigational agent(s) would follow the guidelines for commercial agents. Once therapy with the investigational agent(s) is initiated, all expedited reporting of adverse events should follow the investigational guidelines.

Steps to determine if an adverse event is to be reported in an expedited manner

Step 1: Identify the type of event using the NCI Common Terminology Criteria for Adverse Events (CTCAE). The CTCAE provides descriptive terminology and a grading scale for each adverse event listed. A copy of the CTCAE can be downloaded from the CTEP home page (<http://ctep.cancer.gov>). Additionally, if assistance is needed, the NCI has an Index to the CTCAE that provides help for classifying and locating terms. All appropriate treatment locations should have access to a copy of the CTCAE.

Step 2: Grade the event using the NCI CTCAE version specified.

Step 3: Determine whether the adverse event is related to the protocol therapy (investigational or commercial). Attribution categories are as follows: Unrelated, Unlikely, Possible, Probable, and Definite.

Step 4: Determine the prior experience of the adverse event. Expected events are those that have been previously identified as resulting from administration of the agent. An adverse event is considered *unexpected*, for expedited reporting purposes only, when either the type of event or the severity of the event is not listed in

- the current NCI Agent-Specific Adverse Event List (for treatments using agents provided under an NCI-held IND);
- the drug package insert (for treatments with commercial agents only);
- Section 3.0 of this protocol.

Step 5: Review Table 16.1 in the protocol to determine if there are any protocol-specific requirements for expedited reporting of specific adverse events that require special monitoring.

Step 6: Determine if the protocol treatment given prior to the adverse event included an investigational agent(s), a commercial agent(s), or a combination of investigational and commercial agents.

NOTE: If the patient received at least one dose of investigational agent, follow the guidelines in Table 16.1. If no investigational agent was administered, follow the guidelines in Table 16.2.

NOTE: This includes all events that occur within 30 days of the last dose of protocol treatment. Any event that occurs more than 30 days after the last dose of treatment and is attributed possibly, probably, or definitely to the agent(s) must be reported according to the instructions above.

